- Report patient characteristics by treatment group
- Report summary parameters of study population
- Report median follow-up time by treatment group
- Report reasons for censoring in the overall study population

8. Initial Power Assessment

Action report name:

For apixaban vs. warfarin

Optum- <https://bwh-dope.aetion.com/projects/details/711/results/53838/result/0>

Marketscan- <https://bwh-dope.aetion.com/projects/details/712/results/53839/result/0>

Medicare- <https://bwh-dope.aetion.com/projects/details/713/results/53840/result/0>

Date conducted: 05/12/2020

In order to complete the initial power analysis, the dummy outcome of a 90-day gap in database enrollment will be used. This outcome is used to ensure that no information on the comparative risks of the outcomes of interest are available at this stage. Complete a 1:1 PS-matched comparative analysis using this outcome. PS should include only 3 covariates: age, sex, and combined

comorbidity index. Power calculations are based on the formulas from Chow et al. (2008).

- Stop analyses until feasibility and power are reviewed by primary investigators, FDA, and assigned members of advisory board.

Reviewed by PI:	[name]	Date reviewed:	6/3/20
Reviewed by FDA:	[name]	Date reviewed:	6/30/20
Reasons for stopping analysis (if required):			

9. Balance Assessment

Action report name:

For apixaban vs. warfarin

Optum- <https://bwh-dope.aetion.com/projects/details/711/results/57927/result/0>

Marketscan- <https://bwh-dope.aetion.com/projects/details/712/results/57928/result/0>

Medicare- <https://bwh-dope.aetion.com/projects/details/713/results/57982/result/0>

Date conducted: 8/27/2020 (Medicare 8/30/2020)

After review of initial feasibility and power analyses, complete creation of the remaining covariates (see Table 1 below for list of covariates). Again, using the dummy outcome of a 90-day gap in database enrollment, complete a 1:1 PS-matched analysis. The PS should include the complete list of covariates (excluding laboratory values, which are missing in some patients).

- Provide plot of PS distributions stratified by treatment group.

Note- Please refer to **Appendix B**.

- Report covariate balance after matching.

Note- For Table 1, please refer to **Appendix B**.

- Report reasons for censoring by treatment group.

	Overall	Referent	Exposure
Dummy Outcome	0 (0.00%)	0 (0.00%)	0 (0.00%)
Death	3,281 (1.49%)	1,664 (1.51%)	1,617 (1.47%)

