...mean	3.31 (1.80)	3.52 (1.80)	3.03 (1.71)	3.16 (1.63)	2.07 (1.92)	2.18 (2.00)	3.17 (1.76)	3.37 (1.73)	-0.11
...median [IQR]	3.00 (2.00, 4.00)	3.00 ([2.00, 5.00])	3.00 (2.00, 4.00)	3.00 (2.00, 4.00)	2.00 (0.00, 3.00)	2.00 (1.00, 3.00)			
Frality Score: Qualitative Version 365 days as Categories, v1									
...0; n (%)	14,245 (30.6%)	28,483 (55.1%)	4,407 (9.4%)	13,475 (36.7%)	277,248 (100.0%)	174,898 (100.0%)	295,900 (79.8%)	216,856 (82.4%)	0.00
...1 to 2; n (%)	16,218 (34.9%)	16,697 (32.3%)	19,912 (42.3%)	13,626 (37.1%)	0 (0.0%)	0 (0.0%)	36,139 (9.7%)	30,323 (11.5%)	-0.01
...3 or more; n (%)	16,055 (34.5%)	6,504 (12.6%)	22,768 (48.3%)	9,613 (26.2%)	0 (0.0%)	0 (0.0%)	38,823 (10.5%)	16,117 (6.1%)	0.02
Frality Score: Empirical Version 365 days as Categories, v3									
...<0.1298; n (%)	4,465 (9.6%)	5,291 (10.2%)	4,016 (8.5%)	3,794 (10.3%)	221,855 (80.0%)	143,801 (82.2%)	230,336 (62.1%)	152,886 (58.1%)	0.01
...0.1298 - 0.1631167; n (%)	13,374 (28.8%)	14,905 (28.8%)	12,572 (26.7%)	10,993 (29.9%)	23,931 (8.6%)	14,240 (8.1%)	49,881 (13.5%)	40,138 (15.2%)	0.00
...>0.1631167; n (%)	28,679 (61.7%)	31,488 (60.9%)	30,504 (64.8%)	21,927 (59.7%)	31,462 (11.3%)	16,857 (9.6%)	90,645 (24.4%)	70,722 (26.7%)	0.00
Non-Frality; n (%)	25,223 (54.2%)	29,309 (56.7%)	23,478 (49.9%)	18,490 (50.4%)	5,444 (2.0%)	3,205 (1.8%)	54,145 (14.6%)	51,004 (19.4%)	-0.01
Frality Score (mean): Qualitative Version 365 days, v1									
...mean [sd]	2.1 (2.29)	0.97 (1.59)	2.84 (2.14)	1.65 (1.91)	51 (0.0%)	23 (0.0%)	2.48 (2.22)	1.25 (1.73)	0.62
...median [IQR]	2.00 (0.00, 3.00)	0.00 ([0.00, 1.00])	2.00 (1.00, 4.00)	1.00 (0.00, 3.00)	**	0 (0.0%)			
Frality Score (mean): Empirical Version 365 days, v2									
...mean [sd]	0.19 (0.06)	0.19 (0.06)	0.18 (0.06)	0.18 (0.05)	12.09 ([7.08, 19.38])	10.59 ([5.75, 17.41])	0.18 (0.06)	0.19 (0.06)	-0.17
...median [IQR]	0.18 ([0.15, 0.21])	0.17 ([0.15, 0.21])	0.17 ([0.14, 0.20])	0.17 ([0.14, 0.20])	#REF!	#REF!			
Healthcare Utilization									
Any hospitalization (n)	8,809 (18.9%)	15,564 (30.1%)	11,202 (23.8%)	12,977 (35.3%)	63,143 (22.8%)	60,091 (34.4%)	83,154 (22.4%)	88,632 (33.7%)	-0.02
Any hospitalization during prior 30 days; n (%)	5,453 (12.7%)	9,233 (18.1%)	6,631 (14.4%)	8,475 (23.1%)	36,365 (24.5%)	35,076 (25.5%)	49,414 (21.7%)	53,570 (23.3%)	-0.02
Any hospitalization during prior 31-180 days; n (%)	3,999 (8.8%)	7,277 (14.1%)	5,230 (11.1%)	5,128 (14.0%)	29,055 (14.0%)	29,055 (14.0%)	48,663 (13.8%)	45,477 (15.3%)	-0.01

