...mean	3.50 (1.86)	3.50 (1.84)	3.22 (1.73)	3.20 (1.71)	2.20 (2.00)	2.22 (2.02)	3.36 (1.80)	3.35 (1.78)	0.01
...median [IQR]	3.00 (2.00, 5.00)	3.00 (2.00, 5.00)	3.00 (2.00, 4.00)	3.00 (2.00, 4.00)	2.00 (1.00, 3.00)	2.00 (1.00, 3.00)			
Frailty Score: Qualitative Version 365 days as Categories, v1									
...0; n (%)	6,480 (42.4%)	5,808 (38.0%)	2,847 (19.2%)	2,765 (18.6%)	80,137 (100.0%)	80,137 (100.0%)	89,464 (81.1%)	88,710 (80.5%)	0.00
...1 to 2; n (%)	4,987 (32.7%)	5,444 (35.6%)	5,982 (40.3%)	6,121 (41.2%)	0 (0.0%)	0 (0.0%)	10,969 (9.9%)	11,565 (10.5%)	0.00
...3 or more; n (%)	3,806 (24.9%)	4,021 (26.3%)	6,020 (40.5%)	5,963 (40.2%)	0 (0.0%)	0 (0.0%)	9,826 (8.8%)	9,984 (9.1%)	0.00
Frailty Score: Empirical Version 365 days as Categories, v3									
...<0.12908; n (%)	1,344 (8.8%)	1,533 (10.0%)	1,237 (8.3%)	1,288 (8.7%)	63,958 (79.8%)	63,584 (79.3%)	66,539 (60.3%)	66,405 (60.2%)	0.00
...0.12908 - 0.1631167; n (%)	4,185 (27.4%)	4,252 (27.8%)	4,009 (27.0%)	4,061 (27.3%)	7,169 (8.9%)	7,168 (8.9%)	15,363 (13.9%)	15,481 (14.0%)	0.00
...>0.1631167; n (%)	9,744 (63.8%)	9,488 (62.1%)	9,603 (64.7%)	9,500 (64.0%)	9,910 (11.2%)	9,385 (11.7%)	28,357 (25.7%)	28,373 (25.7%)	0.00
Non-Frailty; n (%)	8,075 (52.9%)	8,222 (53.8%)	7,317 (49.3%)	7,321 (49.3%)	1,831 (2.3%)	1,475 (1.8%)	17,223 (15.6%)	17,018 (15.4%)	0.00
Frailty Score (mean): Qualitative Version 365 days, v1									
...mean [sd]	1.62 (2.14)	1.69 (2.07)	2.40 (2.09)	2.39 (2.08)	0.09 (0.06)	0.09 (0.06)	2.00 (2.12)	2.04 (2.07)	-0.02
Frailty Score (mean): Empirical Version 365 days, v2									
...mean [sd]	0.19 (0.06)	0.19 (0.06)	0.18 (0.05)	0.18 (0.05)	13.79 (10.60)	13.94 (11.23)	0.19 (0.06)	0.19 (0.06)	0.00
...median [IQR]	0.18 (0.15, 0.22)	0.18 (0.15, 0.22)	0.17 (0.15, 0.21)	0.17 (0.15, 0.21)	11.48 (6.52, 18.58)	11.41 (6.24, 18.92)			
Healthcare Utilization									
Any hospitalization (n)									
...Any hospitalization during prior 30 days; n (%)	2,655 (16.4%)	2,680 (16.8%)	3,263 (22.0%)	3,266 (22.0%)	17,754 (20.2%)	17,754 (20.2%)	23,682 (22.7%)	23,695 (22.7%)	0.00
...Any hospitalization during prior 31-180 days; n (%)	1,771 (11.1%)	1,800 (11.5%)	1,943 (12.1%)	1,961 (12.1%)	11,795 (14.0%)	11,795 (14.0%)	15,568 (14.2%)	15,568 (14.2%)	0.00
Endocrinologist Visit; n (%)	423 (2.8%)	422 (2.8%)	485 (3.2%)	480 (3.2%)	3,239 (4.0%)	3,111 (3.9%)	4,337 (3.8%)	4,013 (3.6%)	0.00
Endocrinologist Visit (30 days prior); n (%)	121 (0.8%)	130 (0.9%)	169 (1.1%)	151 (1.0%)	956 (1.2%)	936 (1.2%)	1,246 (1.1%)	1,207 (1.1%)	0.00

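### Table 1 puts every Medicare patient at qualitative frailty score 0, so balance on this score is not shown for 73% of matched pairs

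*Combined protocol and SAP*

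**What the plan says.** Section 9 of the combined protocol and SAP describes the full balance assessment by 1:1 propensity score matching and states: "The PS should include the complete list of covariates (excluding laboratory values, which are missing in some patients". Section 10 then halts the work until the principal investigators, the FDA and assigned advisory board members have reviewed balance and final power. The sign-offs are dated 9/8/20 and 9/29/20.

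The balance evidence is Table 1 in Appendix B. It lists two frailty scores, each as categories and as a mean. The qualitative categories appear in the unmatched table as "Frality Score: Qualitative Version 365 days as Categories, v1" and in the matched table as "Frailty Score: Qualitative Version 365 days as Categories, v1". In both, all Medicare patients fall in category 0, with none in the categories 1 to 2 and 3 or more. The matched pooled cells for category 0 read "89,464 (81.1%) 88,710 (80.5%) 0.00". The documents do not explain the Medicare values.

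**The concern.** Medicare warfarin initiators have a mean age of 77.78 years, against 75.30 in Optum and 74.33 in MarketScan (labelled Truven in the table). Yet only 30.6% of warfarin initiators in Optum and 9.4% in MarketScan score 0, while Medicare shows 100%. A score that is constant in a database can neither inform that database's propensity score nor demonstrate balance there.

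The score matters because, where it varies, it separates the arms more than most rows of the table. Medicare also dominates the pooled analysis, so a gap there affects most of the information in the study. The table that carries the gap is the one on which the Section 10 review was based.

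The second, empirical, frailty score is the natural fallback, but its Medicare distribution also looks out of line: 80.0% of Medicare warfarin initiators are in the lowest category, against 9.6% in Optum and 8.5% in MarketScan.

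**Working it through.** **1. Are the Medicare cells really part of the sponsor's table?** Category 0 of the qualitative score, summed as Optum + MarketScan + Medicare:

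- Unmatched warfarin: 14,245 + 4,407 + 277,248 = 295,900 (printed 295,900)
- Unmatched apixaban: 28,483 + 13,475 + 174,898 = 216,856 (printed 216,856)
- Matched warfarin: 6,480 + 2,847 + 80,137 = 89,464 (printed 89,464)
- Matched apixaban: 5,808 + 2,765 + 80,137 = 88,710 (printed 88,710)

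All four agree exactly, so the 100% is not an artefact of reading the PDF.

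**2. Is the mean row built the same way?** Weighting the Optum and MarketScan means by arm size:

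- Unmatched apixaban: (0.97 × 51,684 + 1.65 × 36,714) / 88,398 = 1.25 (printed 1.25)
- Matched warfarin: (1.62 × 15,273 + 2.40 × 14,849) / 30,122 = 2.00 (printed 2.00)
- Matched apixaban: (1.69 × 15,273 + 2.39 × 14,849) / 30,122 = 2.04 (printed 2.04)

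With Medicare included as zeros, the unmatched apixaban mean would be 110,712 / 263,296 = 0.42. So the pooled mean row omits Medicare and the pooled category rows include it. Before matching, one score therefore shows a printed pooled standardized difference of 0.62 on the mean and 0.00 on category 0.

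**3. How much of the study is affected?** Pairs (Section 10): 15,273 + 14,849 + 80,137 = 110,259, and 80,137 / 110,259 = 72.7%. Expected events (Section 10): 903.95 / 1,115.82 = 81.0%.

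**4. How strongly does the score separate the arms where it varies?** Standardized mean difference (SMD), in absolute value = |pA − pW| / √{[pA(1 − pA) + pW(1 − pW)] / 2}, with W for warfarin and A for apixaban.

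| Database and category | Warfarin | Apixaban | SMD |
|---|---|---|---|
| Optum, 3 or more, unmatched | 16,055/46,518 = 34.5% | 6,504/51,684 = 12.6% | 0.54 |
| MarketScan, 3 or more, unmatched | 22,768/47,096 = 48.3% | 9,613/36,714 = 26.2% | 0.47 |
| Optum, score 0, matched | 42.4% | 38.0% | 0.09 |
| MarketScan, score 0, matched | 19.2% | 18.6% | 0.01 |
| Optum, 3 or more, matched | 24.9% | 26.3% | 0.03 |
| MarketScan, 3 or more, matched | 40.5% | 40.2% | 0.01 |

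In Medicare both variances are zero and the SMD is undefined.

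**5. What do the added zeros do to the pooled rows?** For score 0 before matching, Optum and MarketScan together give 18,652/93,614 = 19.9% against 41,958/88,398 = 47.5%, SMD 0.61. With Medicare added it is 79.8% against 82.4%, SMD 0.07. After matching, the two databases alone give 9,327/30,122 = 31.0% against 8,573/30,122 = 28.5%, SMD 0.055; with Medicare it is 0.017.

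**6. Are neighbouring Medicare cells sound?** Several are not. The unmatched qualitative mean cell holds a count, 51 (0.0%). The matched one holds 0.09 (0.06), which a variable equal to 0 in everyone cannot produce. The unmatched empirical mean cell holds a median with interquartile range, 12.09 (7.08, 19.38), where the other databases show means of 0.18 to 0.19. Matched Medicare calendar time is 365.00 (0.00), and it is carried into the pooled mean: (1,346.50 × 15,273 + 850.64 × 14,849 + 365 × 80,137) / 110,259 = 566.36, as printed.

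**The case against.** A reader might infer three stronger things. The documents support none of them.

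*Frailty is unadjusted in Medicare.* Table 1 is not a list of model terms. Frailty appears in four codings, a separate block is labelled as being for the propensity score, and one row is marked as not added to it. The plan does not say which frailty coding was fitted. The displaced cells in step 6 mean that the row, rather than the variable, may be at fault. Related Medicare covariates are balanced after matching: empirical score in the lowest category 79.8% against 79.3% (SMD 0.01), comorbidity score 2.20 against 2.22, hospitalizations 0.43 against 0.43, hospital days 2.42 against 2.41.

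*The resulting bias favours apixaban.* Warfarin initiators look much frailer only on the qualitative score. On the empirical score, Optum has 61.7% against 60.9% in the top category. In Medicare before matching it is apixaban initiators who have the higher comorbidity score (2.18 against 2.07), more hospitalization (34.4% against 22.8%) and more emergency visits (1.02 against 0.76). Nor does the qualitative score follow age across databases: MarketScan warfarin initiators are younger than Optum's, yet far fewer score 0. Differences in coding could contribute.

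*The pooled matched rows look balanced only because of the Medicare constant.* They remain close without it (SMD 0.055 for score 0), and the matched mean row, which already omits Medicare, shows 2.00 against 2.04.

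These limits stand. They do not answer the remaining point. Balance on the empirical score does not establish balance on the qualitative one, because in Optum the first barely separates the arms and the second separates them widely. The Medicare empirical score itself needs verification.

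**Conclusion.** The defect is real and is confined to what Table 1 can demonstrate. The qualitative frailty score is shown as constant in Medicare, and the pooled rows treat Medicare inconsistently. Balance on this score is therefore not shown for 73% of matched pairs and 81% of expected events. If the variable is constant in the analytic data, the Medicare propensity score cannot have used it, contrary to the intent of Section 9. If only the table is wrong, the Section 10 review was given an incorrect balance table. The documents do not settle which.

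No corrected Medicare figure can be computed, and neither the size nor the direction of an effect on the hazard ratio can be stated. The conclusion assumes that the printed category cells are those that were reviewed, which the exact pooled sums support. Section 13 is blank in this document, so the correction can still be made without knowledge of comparative results.

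**What to change.** Before Section 13, check how both frailty scores were built in the Medicare analytic data, using the code lists and look-back applied in Optum and MarketScan. Then:

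- If the qualitative score is constant in Medicare, correct the build, refit the Medicare propensity score, rematch, and reissue Table 1, the Section 9 summaries and the Section 10 counts.
- If only table cells are misplaced, correct Table 1 and repeat the balance review on the corrected version.
- If the score cannot be computed in Medicare, remove Medicare from its pooled rows, say so, and show Medicare balance on the empirical score once that has been verified.

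In every case, state which frailty coding enters each database's propensity score, and build the pooled category and mean rows from the same databases.

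The cost is some programming, possibly a rerun of the Medicare match with a slightly smaller matched count, and a refreshed review.

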Appendix A

13	Active alcohol or drug abuse, or psychosocial reasons that make study participation impractical	
Measured 180 days prior to and including day of drug initiation in any diagnosis position and inpatient or outpatient care setting
 
Alcohol abuse or dependence ICD-9 diagnosis: 291.xx, 303.xx, 305.0x, 571.0x, 571.1x, 571.2x, 571.3x, 357.5x, 425.5x, E860.0x, V11.3x Drug abuse or dependence ICD-9 diagnosis: 292.xx, 304.xx, 305.2x-305.9x, 648.3x, 965.0x, 967.x, 969.x, 970.81
	
Patorno, Elisabetta et al. "Cardiovascular outcomes associated with canagliflozin versus other non-glipizid antidiabetic drugs: population based cohort study." BMJ 2018;360:k119 http://dx.doi.org/10.1136/bmj.k119
 
Patorno, Elisabetta et al. "Empagliflozin and the Risk of Heart Failure Hospitalization in Routine Clinical Care: A First Analysis from the Empagliflozin Comparative Effectiveness and Safety (EMPRISE) Study." Circulation. 2019 Apr 8. doi: 10.1161/CIRCULATIONAHA.118.039177

14	Recent ischemic stroke (within 7 days)	
Measured 7 days prior to and including day of drug initiation in primary diagnosis position and inpatient care setting
 
Ischemic stroke ICD-9 diagnosis: 433.xx, 434.xx, 436.xx
	
Patorno, Elisabetta et al. "Cardiovascular outcomes associated with canagliflozin versus other non-glipizid antidiabetic drugs: population based cohort study." BMJ 2018;360:k119 http://dx.doi.org/10.1136/bmj.k119
 
Patorno, Elisabetta et al. "Empagliflozin and the Risk of Heart Failure Hospitalization in Routine Clinical Care: A First Analysis from the Empagliflozin Comparative Effectiveness and Safety (EMPRISE) Study." Circulation. 2019 Apr 8. doi: 10.1161/CIRCULATIONAHA.118.039177

15	Severe renal insufficiency (serum creatinine > 2.5 mg/dL or a calculated creatinine clearance < 25 mL/min, See Section 6.3.2.2)	
Measured 180 days prior to and including day of drug initiation in any diagnosis position and inpatient or outpatient care setting
 
CKD stage 4/5/ESRD ICD-9 diagnosis: 585.4x, 585.5x, 585.6x ICD-10 diagnosis: N18.4x, N18.5x, N18.6x
 
OR
 
Dialysis/ Renal transplant code list in sheet "Dialysis and Renal Transplant"
	
16	ALT or AST > 2X ULN or a Total Bilirubin \geq 1.5X ULN (unless an alternative causative factor [e.g., Gilbert's syndrome] is identified)	N/A	

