Appendix A

Dialysis codes
ESRD, defined as 2 codes (either inpatient or outpatient), separated by at least 30 days
Codes include:
- ICD9 prox codes:
39.95, Hemodialysis
54.98, Peritoneal dialysis
- ICD9 dx codes:
585.5x, Chronic kidney disease, Stage V (for ESRD with no mention of dialysis)
585.6x, End stage renal disease (for ESRD with dialysis)
V56.0x, encounter for dialysis NOS
V56.8x, encounter for peritoneal dialysis
V45.1x, renal dialysis status
- CPT4 codes:
90957, 90960, ESRD related services monthly, for patients 12-19 and 20 years of age and older; with 4 or more face-to-face physician visits per month
90958, 90961, ESRD related services monthly, for patients 12-19 and 20 years of age and older; with 2-3 face-to-face physician visits per month
90959, 90962, ESRD related services monthly, for patients 12-19 and 20 years of age and older; with 1 face-to-face physician visit per month
90920, 90921, ESRD related services per full month; for patients 12-19 and twenty years of age and over
90924, 90925, ESRD related services (less than full month), per day; for patients 12-19 and twenty years of age and over
90935, Hemodialysis procedure with single physician evaluation
90937, Hemodialysis procedure requiring repeated evaluation(s) with or without substantial revision of dialysis prescription
90945, Dialysis procedure other than hemodialysis (eg, peritoneal dialysis, hemofiltration, or other continuous renal replacement therapies), with single physician evaluation
90947, Dialysis procedure other than hemodialysis (eg, peritoneal dialysis, hemofiltration, or other continuous renal replacement therapies) requiring repeated physician evaluations, with or without substantial revision of dialysis prescription
90965, 90966, ESRD related services for home dialysis per full month, for patients 12-19 and 20 years of age and older
90969, 90970, ESRD related services for dialysis less than a full month of service, per day; for patients 12-19 and 20 years of age and older
90989, Dialysis training, patient, including helper where applicable, any mode, completed course
90993, Dialysis training, patient, including helper where applicable, any mode, course not completed, per training session
90999, Unlisted dialysis procedure, inpatient or outpatient
99512, Home visit for hemodialysis
- HCPCS codes:
G0257, Unscheduled or emergency dialysis treatment for ESRD patient in a hospital outpatient dept. that is not certified as an ESRD facility

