Diabetes with other ophthalmic manifestations; n (%)											0.00		
Retinal detachment, vitreous hemorrhage; n (%)	70 (0.2%)	105 (0.2%)	394 (0.8%)	152 (0.4%)	1,768 (0.6%)	753 (0.4%)	2,232 (0.6%)	1,010 (0.4%)			0.00		
Retinal detachment, vitreous hemorrhage, retinectomy; n (%)	46 (0.1%)	38 (0.1%)	54 (0.1%)	32 (0.1%)	278 (0.1%)	132 (0.1%)	378 (0.1%)	202 (0.1%)			0.00		
Retinal laser coagulation therapy; n (%)	36 (0.1%)	42 (0.1%)	55 (0.1%)	21 (0.1%)	331 (0.1%)	169 (0.1%)	416 (0.1%)	416 (0.1%)			#VALUE!		
Occurrence of Diabetic Neuropathy v2 Copy; n (%)	2,516 (5.4%)	2,284 (4.4%)	2,055 (4.4%)	1,237 (3.4%)	10,444 (3.8%)	5,519 (2.9%)	15,015 (4.0%)	9,040 (3.4%)			0.00		
Diabetic neuropathy; n (%)											#VALUE!		
Diabetic neuropathy v2; n (%)	0 (0.0%)	0 (0.0%)	0 (0.0%)	0 (0.0%)	0 (0.0%)	0 (0.0%)	0 (0.0%)	0 (0.0%)			0.00		
Diabetic neuropathy v2; n (%)	262 (0.8%)	145 (0.3%)	522 (1.1%)	168 (0.5%)	2,539 (1.2%)	1,249 (1.3%)	4,424 (1.7%)	2,662 (0.9%)			0.00		
Hyperglycemia; n (%)	2,214 (4.8%)	3,478 (6.7%)	1,225 (2.6%)	1,520 (4.1%)	14,278 (5.1%)	12,139 (6.9%)	17,715 (4.8%)	17,137 (6.5%)			-0.01		
Disorders of fluid electrolyte and acid-base balance; n (%)													
Diabetic ketoacidosis; n (%)	3,947 (8.5%)	6,950 (13.4%)	3,246 (6.9%)	3,753 (10.2%)	20,433 (7.4%)	9,603 (9.3%)	27,626 (7.4%)	20,306 (7.7%)			0.00		
Hyperosmolar hyperglycemic nonketotic syndrome (HHS); n (%)	38 (0.1%)	27 (0.1%)	48 (0.1%)	28 (0.1%)	26,016 (0.1%)	14,020 (0.1%)	352 (0.1%)	197 (0.1%)			0.00		
Diabetes mellitus without mention of complications; n (%)											0.00		
Hypertension: 1 inpatient or 2 outpatient claims within 365 days; n (%)	12,418 (26.7%)	11,942 (23.1%)	12,169 (25.8%)	8,307 (22.6%)	72,769 (26.2%)	39,895 (22.8%)	97,356 (26.3%)	60,144 (22.8%)			0.01		
Hypertension v2; n (%)	38,202 (82.1%)	31,513 (61.0%)	22,282 (47.3%)	30,224 (82.3%)	240,781 (86.8%)	156,352 (89.4%)	31,340 (84.7%)	231,515 (87.9%)			0.00		
Hypertension v2; n (%)	26,248 (56.4%)	5,000 (1.0%)	4,232 (0.8%)	3,423 (0.8%)	22,434 (0.8%)	15,113 (0.8%)	31,340 (0.8%)	24,776 (0.8%)			0.00		
Renal dysfunction (non-diabetic); n (%)	33 (0.1%)	33 (0.1%)	36 (0.1%)	16 (0.0%)	140 (0.1%)	91 (0.1%)	146 (0.1%)	140 (0.1%)			#VALUE!		
Occurrence of acute renal disease v2; n (%)	27 (0.1%)	23 (0.1%)	31 (0.1%)	13 (0.0%)	102 (0.0%)	74 (0.0%)	**	**			#VALUE!		
Occurrence of chronic renal insufficiency; n (%)	0 (0.0%)	0 (0.0%)	0 (0.0%)	0 (0.0%)	0 (0.0%)	0 (0.0%)	0 (0.0%)	0 (0.0%)			#VALUE!		

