Chronic kidney disease v2; n (%)	0 (0.0%)	0 (0.0%)	0 (0.0%)	0 (0.0%)	0 (0.0%)	0 (0.0%)	0 (0.0%)	0 (0.0%)			#VALUE!		
CKD Stage 3-4; n (%)	0 (0.0%)	0 (0.0%)	0 (0.0%)	0 (0.0%)	0 (0.0%)	0 (0.0%)	0 (0.0%)	0 (0.0%)			#VALUE!		
Occurrence of hypertensive nephropathy; n (%)	0												

Table 1: Unmatched

Linagliptin; n (%)	76 (0.2%)	128 (0.2%)	125 (0.3%)	106 (0.3%)	0.00 [0.00, 0.00]	0.00 [0.00, 0.00]	#VALUE!	#VALUE!	#VALUE!
Saxagliptin; n (%)	130 (0.3%)	115 (0.2%)	164 (0.3%)	76 (0.2%)	0	0	#VALUE!	#VALUE!	#VALUE!
Sitagliptin; n (%)	519 (1.1%)	513 (1.0%)	1,048 (2.2%)	603 (1.6%)	0.08 (0.40)	0.10 (0.44)	1,567 (0.4%)	1116 (0.4%)	0.00
Concomitant initiation or current use of 2nd Generation AGIs; n (%)	2,811 (6.0%)	2,013 (3.9%)	2,878 (6.1%)	1,524 (4.2%)	222 (0.1%)	87 (0.0%)	5,911 (1.6%)	3,624 (1.4%)	0.00
Concomitant initiation or current use of AGIs; n (%)	22 (0.0%)	20 (0.0%)	20 (0.0%)	20 (0.1%)	85 (0.0%)	59 (0.0%)	127 (0.0%)	99 (0.0%)	#DIV/0!
Concomitant initiation or current use of Glitazones; n (%)	296 (0.6%)	383 (0.7%)	394 (0.8%)	295 (0.8%)	10,008 (3.6%)	4,508 (2.6%)	10,698 (2.9%)	5,186 (2.0%)	0.01
Concomitant initiation or current use of Insulin; n (%)	175 (0.4%)	313 (0.6%)	295 (0.6%)	325 (0.9%)	75 (0.0%)	24 (0.0%)	#VALUE!	#VALUE!	#VALUE!
Concomitant initiation or current use of Meglitinides; n (%)	1,335 (2.9%)	1,061 (2.1%)	1,855 (3.9%)	943 (2.6%)	5,097 (1.8%)	1,483 (0.8%)	8,287 (2.2%)	3,487 (1.3%)	0.01
Concomitant initiation or current use of Metformin; n (%)	41 (0.1%)	46 (0.1%)	147 (0.3%)	61 (0.2%)	0	0	#VALUE!	#VALUE!	#VALUE!
Use of 2nd Generation Sulfonylureas; n (%)	5,447 (11.7%)	5,502 (10.6%)	5,060 (10.7%)	3,953 (10.8%)	0.09 (0.06)	0.08 (0.06)	10,507 (2.8%)	9,455 (3.6%)	0.00
Pat use of 2nd Generation Sulfonylureas; n (%)	536 (1.2%)	437 (0.8%)	638 (1.4%)	322 (0.9%)	**	**	#VALUE!	#VALUE!	#VALUE!
Pat use of AGIs Copy; n (%)	**	**	17 (0.0%)	**	**	**	#VALUE!	#VALUE!	#VALUE!
Pat use of Glitazones Copy; n (%)	90 (0.2%)	80 (0.2%)	100 (0.2%)	78 (0.2%)	40 (0.0%)	19 (0.0%)	#VALUE!	#VALUE!	#VALUE!
Pat use of GLP-1 Receptor Agonists; n (%)	96 (0.2%)	119 (0.2%)	113 (0.3%)	122 (0.3%)	**	**	#VALUE!	#VALUE!	#VALUE!
Pat use of Insulin Copy; n (%)	593 (1.3%)	410 (0.8%)	630 (1.3%)	324 (0.9%)	42 (0.0%)	21 (0.0%)	1,246 (3.0%)	755 (0.3%)	0.00
Pat use of Meglitinides Copy; n (%)	26 (0.1%)	12 (0.0%)	40 (0.1%)	23 (0.1%)	0	0	#VALUE!	#VALUE!	#VALUE!

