Hyperosmolar hyperglycemic nonketotic syndrome (HHS); n (%)	18 (0.1%)	15 (0.1%)	16 (0.1%)	**	71 (0.1%)	74 (0.1%)	105 (0.1%)	#VALUE!	#VALUE!
Diabetes mellitus without mention of complications; n (%)									
n (%)	3,809 (24.9%)	3,816 (25.0%)	3,576 (24.1%)	3,582 (24.1%)	20,010 (25.0%)	20,230 (25.2%)	27,395 (24.8%)	27,628 (25.1%)	0.00
Within 365 days; n (%)	13,001 (85.1%)	12,934 (84.7%)	11,752 (79.1%)	11,730 (79.0%)	71,353 (89.0%)	71,353 (89.0%)	96,163 (87.7%)	96,017 (87.1%)	0.00
Hyperglycemia v2; n (%)	9,005 (59.0%)	7,798 (52.5%)	7,774 (52.4%)	41,925 (33.3%)	70,869 (38.0%)	71,404 (32.8%)	104,000 (33.3%)	103,437 (33.5%)	0.00
Diabetes mellitus v2; n (%)	1,843 (12.1%)	1,485 (10.0%)	1,405 (7.6%)	1,405 (7.6%)	7,090 (5.1%)	7,090 (5.1%)	9,074 (5.1%)	9,074 (5.1%)	0.00
Renal dysfunction (non-diabetic) v2; n (%)	15 (0.1%)	**	12 (0.1%)	55 (0.1%)	49 (0.1%)	49 (0.1%)	#VALUE!	#VALUE!	#VALUE!
Occurrence of acute renal disease v2; n (%)	12 (0.1%)	**	11 (0.1%)	46 (0.1%)	42 (0.1%)	42 (0.1%)	#VALUE!	#VALUE!	#VALUE!
Occurrence of chronic renal insufficiency; n (%)	0 (0.0%)	0 (0.0%)	0 (0.0%)	0 (0.0%)	0 (0.0%)	0 (0.0%)	0 (0.0%)	0 (0.0%)	#VALUE!
Chronic kidney disease v2; n (%)	0 (0.0%)	0 (0.0%)	0 (0.0%)	0 (0.0%)	0 (0.0%)	0 (0.0%)	0 (0.0%)	0 (0.0%)	#VALUE!
CKD Stage 3-4; n (%)	0 (0.0%)	0 (0.0%)	0 (0.0%)	0 (0.0%)	0 (0.0%)	0 (0.0%)	0 (0.0%)	0 (0.0%)	#VALUE!
Occurrence of hypertensive nephropathy; n (%)	0 (0.0%)	0 (0.0%)	0 (0.0%)	0 (0.0%)	0 (0.0%)	0 (0.0%)	0 (0.0%)	0 (0.0%)	#VALUE!
Occurrence of miscellaneous renal insufficiency v2; n (%)	**	**	**	**	6 (0.0%)	6 (0.0%)	#VALUE!	#VALUE!	#VALUE!
Glaucoma or cataracts v2; n (%)	2,873 (18.8%)	3,064 (20.1%)	2,941 (19.8%)	2,840 (19.2%)	16,717 (20.9%)	16,763 (20.6%)	22,641 (20.5%)	22,768 (20.6%)	0.00
Cellulitis or abscess of face; n (%)	294 (1.9%)	198 (1.3%)	195 (1.3%)	1108 (1.4%)	1,212 (1.5%)	1,270 (1.4%)	1,770 (1.5%)	1,770 (1.5%)	0.00
Foot ulcer; n (%)	322 (2.1%)	323 (2.1%)	345 (2.3%)	304 (2.0%)	1,810 (2.3%)	1,795 (2.2%)	2,477 (2.2%)	2,422 (2.2%)	0.00
Bladder stones; n (%)	18 (0.1%)	27 (0.2%)	19 (0.1%)	32 (0.2%)	79 (0.1%)	105 (0.1%)	116 (0.1%)	164 (0.1%)	0.00
Kidney stones; n (%)	222 (1.5%)	225 (1.5%)	253 (1.7%)	275 (1.9%)	1,205 (1.5%)	1,230 (1.5%)	1,680 (1.5%)	1,730 (1.6%)	0.00
Urinary tract infection (UTI); n (%)	1,543 (10.1%)	1,671 (10.9%)	1,230 (8.3%)	1,255 (8.5%)	10,192 (12.7%)	10,461 (13.1%)	12,965 (11.8%)	13,387 (12.1%)	0.00
Urinary tract infection; n (%)	4,469 (29.3%)</								

Table 1: Matched

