Lab values- BUN (mg/dl) within 3 months; n (%)	2,953 (19.3%)	3,245 (21.2%)	181 (1.2%)	155 (1.0%)	N/A	N/A	3,134 (10.4%)	3,400 (11.3%)	0.00
Lab values- BUN (mg/dl) within 6 months; n (%)	3,435 (28.4%)	4,694 (30.7%)	258 (1.7%)	231 (1.6%)	N/A	N/A	4,603 (15.3%)	4,925 (16.4%)	0.00
Lab values- Creatinine (mg/dl); v2; n (%)	4,447 (29.1%)	4,846 (31.7%)	273 (1.8%)	237 (1.6%)	N/A	N/A	4,720 (15.7%)	5,083 (16.9%)	0.00
Lab values- Creatinine (mg/dl); v2; n (%)	3,016 (19.7%)	3,373 (22.1%)	191 (1.3%)	157 (1.1%)	N/A	N/A	3,207 (10.6%)	3,530 (11.7%)	0.00
Lab values- Creatinine (mg/dl) within 6 months; v2; n (%)	4,447 (29.1%)	4,846 (31.7%)	273 (1.8%)	237 (1.6%)	N/A	N/A	4,720 (15.7%)	5,083 (16.9%)	0.00
Lab values- HDL level (mg/dl); n (%)	2,935 (19.2%)	3,065 (20.1%)	175 (1.2%)	140 (0.9%)	N/A	N/A	3,110 (10.3%)	3,205 (10.6%)	0.00
Lab values- LDL level (mg/dl); v2; n (%)	3,142 (20.6%)	3,273 (21.4%)	192 (1.3%)	139 (0.9%)	N/A	N/A	3,207 (10.6%)	3,330 (11.7%)	0.00
Lab values- LDL level (mg/dl); within 3 months; n (%)	3,142 (20.6%)	3,273 (21.4%)	192 (1.3%)	139 (0.9%)	N/A	N/A	3,207 (10.6%)	3,330 (11.7%)	0.00
Lab values- LDL level (mg/dl); within 6 months; n (%)	3,142 (20.6%)	3,273 (21.4%)	192 (1.3%)	139 (0.9%)	N/A	N/A	3,207 (10.6%)	3,330 (11.7%)	0.00
Lab values- LDL level (mg/dl); v2; n (%)	1,887 (12.4%)	1,978 (13.0%)	114 (0.8%)	82 (0.6%)	N/A	N/A	2,001 (6.6%)	2,060 (6.8%)	0.00
Lab values- LDL cholesterol (mg/dl); within 6 months; v2; n (%)	3,142 (20.6%)	3,273 (21.4%)	192 (1.3%)	139 (0.9%)	N/A	N/A	3,334 (11.1%)	3,412 (11.3%)	0.00
Lab values- NT-proBNP; n (%)	42 (0.3%)	61 (0.4%)	**	**	N/A	N/A	#VALUE!	#VALUE!	#VALUE!
Lab values- NT-proBNP; within 3 months; n (%)	34 (0.2%)	44 (0.3%)	**	**	N/A	N/A	#VALUE!	#VALUE!	#VALUE!
Lab values- NT-proBNP; within 6 months; n (%)	42 (0.3%)	61 (0.4%)	**	**	N/A	N/A	#VALUE!	#VALUE!	#VALUE!
Lab values- Total cholesterol (mg/dl); v2; n (%)	3,012 (19.7%)	3,125 (20.5%)	174 (1.2%)	137 (0.9%)	N/A	N/A	3,186 (10.6%)	3,262 (10.8%)	0.00
Lab values- Triglyceride level (mg/dl); n (%)	2,951 (11.6%)	1,870 (12.2%)	98 (0.7%)	80 (0.5%)	N/A	N/A	1,869 (6.6%)	1,950 (6.5%)	0.00
Lab values- Triglyceride level (mg/dl); within 3 months; n (%)	2,951 (19.3%)	3,091 (20.2%)	171 (1.2%)	139 (0.9%)	N/A	N/A	3,122 (10.4%)	3,230 (10.7%)	0.00
Lab values- Triglyceride level (mg/dl); within 6 months; n (%)	2,951 (19.3%)	3,091 (20.2%)	171 (1.2%)	139 (0.9%)	N/A	N/A	3,122 (10.4%)	3,230 (10.7%)	0.00

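### Exclusion 15 as printed keeps CKD stages 1-3 and unspecified CKD eligible, yet Table 1 prints zero CKD in every arm and database; codes, covariates and table must be reconciled before Section 13

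*Combined protocol and SAP*

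**What the plan says.** Appendix A, Exclusion 15 adapts the trial's severe renal insufficiency criterion. It uses diagnosis codes in the 180 days up to and including drug initiation: "ICD-9 diagnosis: 585.4x, 585.5x, 585.6x ICD-10 diagnosis: N18.4x, N18.5x, N18.6x". Dialysis or renal transplant, from a separate code sheet, is the alternative route. The only CKD diagnosis codes on that sheet are for stage 5 and ESRD, for example "585.5x, Chronic kidney disease, Stage V (for ESRD with no mention of dialysis". No other exclusion in Appendix A names CKD.

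Appendix B, Table 1 carries three chronic renal rows in both its unmatched and matched versions: "Occurrence of chronic renal insufficiency; n" (%), "Chronic kidney disease v2; n" (%) and CKD Stage 3-4. All three print 0 (0.0%) in every column of both versions. The matched For PS block at the end of the table has a row for chronic renal insufficiency without CKD, and it is also zero throughout.

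Section 9 puts the complete covariate list into the propensity score (PS), except laboratory values. Section 10 holds the analysis until balance has been reviewed. It records review dates and no reason for stopping. Section 13 (comparative analyses) is undated.

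**The concern.** The exclusion and the balance table describe different cohorts. The printed codes admit CKD stages 1-3 and unspecified CKD, and Table 1 and its For PS block carry rows for CKD Stage 3-4 and CKD Stage 1-2. Those rows make sense only if such patients can be present. Yet none appear, even before matching.

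Three causes are possible, and what is at stake differs:

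- The executed exclusion was broader than Appendix A. The cohort is then not the one the plan defines, and is narrower than the trial criterion it adapts.
- The CKD covariates are empty. CKD then has no influence on the PS or the matching, and its balance has not been shown.
- The table is faulty. Only the table needs correcting.

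**Working it through.** **1. The exclusion step (Section 5.3 flowchart).** The printed counts reproduce:

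- Optum: 109,560 − 9,885 = 99,675
- MarketScan (Truven): 90,400 − 5,151 = 85,249
- Medicare: 512,355 − 50,219 = 462,136

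In all, 65,255 of 712,315 patients were removed (9.2%). The flowchart gives no breakdown by code.

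**2. Denominators (Table 1 column heads).**

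- Unmatched: 46,518 + 51,684 + 47,096 + 36,714 + 277,248 + 174,898 = 634,158. The flowchart's final cohorts total 98,328 + 83,916 + 452,699 = 634,943, or 785 more; this does not affect the point.
- Matched: 2 × (15,273 + 14,849 + 80,137) = 2 × 110,259 = 220,518.

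**3. The zeros.** Each of the three rows has six database-by-arm cells and two pooled cells: 3 rows × 8 cells × 2 tables = 48 cells, all 0 (0.0%). The matched For PS row adds eight more. In the CKD Stage 3-4 row, the stage 4 part should be zero because Exclusion 15 removes it; the stage 3 part should not. The matched For PS row for CKD Stage 1-2 is cut after its first cell in the text available, so it is not relied on.

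**4. Could the zeros be chance?** Read as real counts, 0 of n has an exact one-sided 95% upper bound of 1 − 0.05^(1/n):

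- n = 634,158: 4.7 per million
- n = 220,518: 13.6 per million

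The documents give no CKD prevalence, so the range below is an assumption:

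| Assumed prevalence of eligible CKD | Expected unmatched | Expected matched |
|---|---|---|
| 0.01% | 63 | 22 |
| 0.1% | 634 | 221 |
| 1% | 6,342 | 2,205 |
| 10% | 63,416 | 22,052 |

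Even at 0.01%, about 63 unmatched cases would be expected. Chance does not explain the zeros.

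**5. Could another row show renal balance?** Recorded creatinine ("Lab values- Creatinine (mg/dl); v2; n" (%), matched) cannot stand in for CKD:

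- Optum: 4,447/15,273 = 29.1% and 4,846/15,273 = 31.7%
- MarketScan: 273/14,849 = 1.8% and 237/14,849 = 1.6%
- Medicare: not available, and Medicare is 160,274/220,518 = 72.7% of the matched cohort

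**The case against.** The strongest reply is that this part of the table cannot be trusted. Neighbouring renal rows have lost or repeated cells, and some pooled cells do not equal the sum of the databases. That some nearby rows add up, such as "Kidney stones; n" (%) (222 + 253 + 1,205 = 1,680), does not authenticate rows made only of zeros. The standardized-difference column does not help either: all-zero rows show #VALUE! in the CKD rows, a division-by-zero code in the For PS row and 0.00 in an unmatched diabetic neuropathy row. In addition, no renal covariate definition is printed, and the full ICD-10 lists are in an external folder.

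Much of this stands, and it is why a table fault remains open and confidence is medium. It does not remove the conflict. The rows in question are complete and identical in two tables, the zeros recur in the For PS block, suppressed cells print as ** rather than 0, and the ICD-10 diagnosis codes of Exclusion 15 are printed in Appendix A.

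A reader might infer that the executed exclusion was broader than printed, because two unmatched renal rows are also nearly empty. "Occurrence of acute renal disease v2; n" (%) totals 27 + 23 + 31 + 13 + 102 + 74 = 270 (0.04%), and "Renal dysfunction (non-diabetic); n" (%) totals 33 + 33 + 36 + 16 + 140 + 91 = 349 (0.06%). The documents do not support that step:

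- The pooled cells of the first row print ** although all six database cells are shown.
- The pooled warfarin cell of the second prints 146 against 33 + 36 + 140 = 209.
- Nothing says that one row contains the other, so their difference of 79 has no defined meaning.
- Faulty covariate code lists would give the same pattern.

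Nor do the 65,255 patients removed measure the problem. That is the whole exclusion step, including everyone properly removed.

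**Conclusion.** The conflict holds: the printed exclusion leaves CKD stages 1-3 and unspecified CKD eligible, and three CKD rows show none among 634,158 unmatched or 220,518 matched patients. At least one of Exclusion 15 as printed, the codes or covariates as executed, and Table 1 is wrong.

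The documents do not show which, and no cause is favoured. A reader might go further and infer a biased hazard ratio. That is not supported: a narrower population is not in itself a bias, a table fault has no effect on the estimate, and even with empty covariates the documents give no CKD prevalence by arm from which to size an effect. What can be said is conditional. If the covariates are empty, CKD plays no part in a PS that also excludes laboratory values, and the reviewed balance table says nothing about it.

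The conclusion assumes that the 48 zero cells are as issued and that eligible CKD is not vanishingly rare in this cohort. It should be fixed before the comparative analyses; confidence is medium.

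**What to change.** Before Section 13:

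1. Check the renal rows of both Table 1 versions, and of the For PS block, against the source output.
2. Count patients with CKD stage 1-3 and unspecified CKD codes just before and just after the Exclusion 15 step. State the executed codes for that step and for each renal covariate.

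Then act on the result:

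- If the step removed these patients, reconcile the executed codes with Appendix A: either re-run with the printed codes, or correct Appendix A and disclose the narrower population.
- If the patients remain but the covariates are empty, repair the covariates, re-estimate the PS and re-match.
- If only the table is wrong, correct it.

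Reissue Table 1 and, if the matched number changes, the Section 10 power table.

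The diagnosis costs one source check and two counts in the platform. The remedy ranges from a text or table correction to a re-run of cohort assembly, PS and matching. No new data are needed.
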